7.6 Rash (including photosensitivity conditions)

Subjects should be informed that they should contact their doctor immediately when they notice any skin reaction. The skin reaction should be evaluated in the clinic the same day (if possible) or the next day.

Photosensitivity conditions fall under the general umbrella of rash events. However, photosensitivity reactions can be differentiated from other rash events by careful history taking and general physical examination. Photosensitivity skin reactions are typically triggered by prolonged or extreme exposure to sunlight or artificial light. These reactions may present as an exaggerated sunburn reaction, usually affecting areas exposed to light (typically the face, ‘V’ area of the neck, extensor surfaces of the forearms, and the dorsa of the hands). Photosensitivity reactions can be prevented by avoiding excessive sun exposure and by the use of sun protection measures.

All rash events should be captured in the Adverse Event Section of the eCRF. A separate Rash page will be completed in case of a rash event. For rash events considered as potential photosensitivity reaction, a separate Photosensitivity page will be completed.

Monitoring of the evolution of rash (including photosensitivity reactions) will be performed based on the grade (severity) of the rash. At the discretion of the investigator, additional visits and assessments can be performed. Management of rash will take into account the protocol-defined procedures outlined in [Table 7-1](#).

Discontinuation of SMV should be considered if a photosensitivity reaction occurs and subjects should be monitored until the reaction has resolved. If a decision is made to continue SMV in the setting of a photosensitivity reaction, expert consultation is advised.

Table 7-1. Guidelines for Subjects Developing Rash Grade 1 to Grade 4

WHO Grade	Rash Definition	Investigator Action
Grade 1 Rash (with or without pruritus) ^a	Erythema	May continue intake of study drugs at the investigator’s discretion.
Grade 2 Rash (with or without pruritus) ^b	diffuse, maculopapular rash, OR dry desquamation	May continue intake of study drugs at the investigator’s discretion.
Grade 3 Rash	
 • vesiculation, moist desquamation, or ulceration OR • any cutaneous event with one of the following: 
 - elevations in AST/ALT >2× baseline value - fever >38°C or 100°F - eosinophils >1.00 ×10³/μL 	Permanently discontinue the intake of SMV. May continue intake of ODV and AL-335 at the investigator’s discretion. No rechallenge is allowed.
Grade 4 Rash	exfoliative dermatitis, OR 
 • mucous membrane involvement, OR • erythema multiforme major, OR • Stevens-Johnson Syndrome, OR • necrosis requiring surgery 	Permanently discontinue the intake of all study drugs. No rechallenge is allowed.

^a In case the rash evolves from a Grade 1 to a higher grade, management of the rash should follow the guidelines

indicated for Grade 2 or Grade 3 or 4 rash, respectively

- ^b In case the rash evolves from a Grade 2 to a Grade 3 or 4 rash, management of the rash should follow the guidelines specified for Grade 3 or 4 rash.
- ^c Monotherapy with any of the study drugs is not allowed.

When safety blood samples are drawn as per the rash management guidelines, these should be processed by the local laboratory; a separate blood sample should also be sent for central laboratory confirmation. The following parameters will need to be tested: AST, ALT, sedimentation rate, complete blood cell count (including hemoglobin, hematocrit, red blood cell count, white blood cell count, platelet count, neutrophils, lymphocytes, monocytes, eosinophils and basophils) and creatinine. The values of the local laboratory assessments need to be transcribed in the eCRF by the study-site personnel.

The subject may be treated symptomatically until the rash resolves. Oral antihistamines (e.g., cetirizine, levocetirizine) and/or topical corticosteroids may provide symptomatic relief but effectiveness of these measures has not been established. If systemic corticosteroids for longer than 24 hours are required for treatment of rash, the study drugs need to be permanently discontinued. If the rash is considered to be most likely due to concomitant illness or non-study drugs, standard management, including discontinuation of the likely causative agent, should be undertaken.

Dermatologist fees for evaluating subjects who experience a rash during the study will be reimbursed by the Sponsor.

The following grades are based on the WHO Toxicity Grading Scale.

Grade 1 Rash (with or without pruritus)

A Grade 1 rash is defined as **erythema**.

- Subjects may continue the intake of study drugs (at the investigator's discretion).
- An unscheduled visit may be performed at the investigator's discretion as soon as possible after the subject contacts the investigator to report the AE.
- Assessment of safety blood samples by the local laboratory is recommended. The values of the local laboratory assessments need to be transcribed in the eCRF by the study-site personnel.

Unscheduled visits may also be performed after the initial rash assessment at the investigator's discretion for appropriate follow up until resolution of the rash. At these visits, safety blood samples can be taken at the investigator's discretion. For these and all subsequent local laboratory blood sample assessments, the values of the assessments need to be transcribed in the eCRF by the study-site personnel.

The subject should be advised to contact the investigator immediately if there is any worsening of the rash, if any systemic signs or symptoms appear, or if mucosal involvement develops. If appropriate, sun protection counseling should be provided.

In case the rash evolves from a Grade 1 to a higher grade, management of the rash should follow the guidelines indicated for Grade 2 or Grades 3 to 4 rash, respectively.

Grade 2 Rash (with or without pruritus)

A Grade 2 rash is defined as diffuse, maculopapular rash OR dry desquamation.

- Subjects may continue the intake of study drugs (at the investigator's discretion).
- An unscheduled visit for initial rash evaluation is required as soon as possible after the subject contacts the investigator to report the AE. If a visit is not possible, telephone contact with the subject should take place to collect information and to give advice on the necessary measures to be taken.
- Assessment of safety blood samples by the local laboratory is recommended. The values of the local laboratory assessments need to be transcribed in the eCRF by the study-site personnel.
- Referral to a dermatologist is optional but, when done, should occur preferably within 24 hours after the onset of the rash. A copy of the dermatologist's report should be made anonymous and will be collected by the monitor.

Unscheduled visits will also be performed after the initial rash assessment at the investigator's discretion for appropriate follow up until resolution of the rash. At these visits, safety blood samples must be taken. For these and all subsequent local laboratory blood sample assessments, the values of the assessments need to be transcribed in the eCRF by the study-site personnel.

The subject should be advised to contact the investigator immediately if there is any worsening of the rash, if any systemic signs or symptoms appear, or if mucosal involvement develops. If appropriate, sun protection counseling should be provided.

In case the rash evolves from a Grade 2 to a Grade 3 to 4 rash, management of the rash should follow the guidelines specified for Grade 3 to 4 rash.

Grade 3 or Grade 4 Rash

A Grade 3 rash is defined as a rash associated with:

- vesiculation, moist desquamation, or ulceration OR
- any cutaneous event with one of the following:
 - elevations in AST/ALT $>2\times$ baseline value
 - fever $>38^{\circ}\text{C}$ or 100°F
 - eosinophils $>1.00\times 10^3/\mu\text{L}$
 - serum sickness-like reaction

Subjects will permanently discontinue SMV and may continue ODV and AL-335 (monotherapy with any of the study drugs is not allowed). No rechallenge is allowed.

A Grade 4 rash is defined as:

- exfoliative dermatitis, OR
- mucous membrane involvement, OR
- erythema multiforme major, OR
- Stevens-Johnson Syndrome, OR
- necrosis requiring surgery

Subjects will permanently discontinue all study drugs. No rechallenge is allowed.

An unscheduled (on-site) visit including a safety laboratory evaluation is required as soon as possible after the subject contacts the investigator to report the AE.

Assessment of safety blood samples by the local laboratory is required on the day of initial rash evaluation and the day thereafter (Days 0 and 1). The values of the local laboratory assessments need to be transcribed in the eCRF by the study-site personnel.

Referral to a dermatologist is required, preferably within 24 hours after the onset of the rash. A copy of the dermatologist report should be made anonymous and be collected by the monitor.

A biopsy may be performed at the discretion of the dermatologist for Grade 3 rash and is required in case of a Grade 4 rash as soon as possible after onset of rash. A copy of the dermatologist's report, and the biopsy if performed, should be made anonymous and be collected by the monitor.

Appropriate management should be undertaken and subjects should be followed until resolution of the rash or until clinical stability is reached.

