4.6.1 Subject Treatment Discontinuation Criteria

If a subject's study drug treatment must be discontinued before the end of the treatment regimen, this will not result in automatic withdrawal of the subject from the study.

A subject's study drug treatment (AL-335, SMV and ODV) must be permanently discontinued if:

- The investigator believes that for safety reasons (e.g., AE), it is in the best interest of the subject to discontinue study drug treatment.
- The subject becomes pregnant.
- The subject has evidence of muscle injury (Section 7.5.1) or cardiac toxicity (Section 7.5.2 and 7.5.3).
- The subject has a Grade 4 rash; see Section 7.6.
- The subject has a Grade 3 or 4 allergic reaction; see Section 7.7.
- The subject has a confirmed Grade 4 ALT and/or AST value that is $>2\times$ the baseline value; see Section 7.9.
- The subject has a confirmed Grade 4 bilirubin value which is considered a sign of worsening liver disease, or for which there is no identifiable explanation; see Sections 7.8 and 7.9.
- The subject has severe worsening of hepatic disease.
- The subject has a confirmed diagnosis of pancreatitis.
- The subject has a Grade 4 AE or laboratory abnormality at least possibly related to 1 of the study drugs and which is considered clinically significant (laboratory abnormalities only).
- The subject requires treatment with any of the medications reported on the list of disallowed medications; see Section 5.12.
- The subject experiences inadequate virologic response or viral breakthrough (refer to Definitions)
- An event occurs which triggers the study treatment stopping criteria (Section 4.7.1)

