If the severity of an AE could fall in either one of two grades (i.e., the severity of an AE could be either grade 2 or grade 3), sites should select the higher of the two grades.

Laboratory Values

General. An asymptomatic, abnormal laboratory finding without an accompanying AE should not be reported to DAIDS in an expedited timeframe unless it meets protocol-specific reporting requirements. Sites should refer to the applicable network standards for reporting abnormal laboratory findings on the CRFs.

Values below Grade 1. Any laboratory value that is between the ULN and grade 1 (for high values) or the LLN and grade 1 (for low values) should not be graded or reported as an AE. Sites should consult the *Manual for Expedited Reporting of Adverse Events to DAIDS, Version 2.0* and their protocol when making an assessment of the need to report an AE.

Overlap of Local Laboratory Normal Values with Grading Table Ranges. When local laboratory normal values fall within grading table laboratory ranges, the severity grading is based on the ranges in the grading table unless there is a protocol-specific grading criterion for the laboratory

Instructions for Use

value. For example, "Magnesium, Low" has a grade 1 range of 1.2 to < 1.4 mEq/L, while a particular laboratory's normal range for magnesium may be 1.3 to 2.8 mEq/L. If a study participant's magnesium laboratory value is 1.3 mEq/L, the laboratory value should be graded as grade 1.

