Cytokine Release Syndrome⁹	Mild signs and symptoms AND Therapy (i.e., antibody infusion) interruption not indicated	Therapy (i.e., antibody infusion) interruption indicated AND Responds promptly to symptomatic treatment OR Prophylactic medications indicated for ≤ 24 hours	Prolonged severe signs and symptoms OR Recurrence of symptoms following initial improvement	Life-threatening consequences (e.g., requiring pressor or ventilator support)
Fatigue or Malaise Report only one	Symptoms causing no or minimal interference with usual social & functional activities	Symptoms causing greater than minimal interference with usual social & functional activities	Symptoms causing inability to perform usual social & functional activities	Incapacitating symptoms of fatigue or malaise causing inability to perform basic self-care functions
Fever (non-axillary temperatures only)	38.0 to < 38.6°C or 100.4 to < 101.5°F	≥ 38.6 to < 39.3°C or ≥ 101.5 to < 102.7°F	≥ 39.3 to < 40.0°C or ≥ 102.7 to < 104.0°F	≥ 40.0°C or ≥ 104.0°F
Pain¹⁰ (not associated with study agent injections and not specified elsewhere) Specify location	Pain causing no or minimal interference with usual social & functional activities	Pain causing greater than minimal interference with usual social & functional activities	Pain causing inability to perform usual social & functional activities	Disabling pain causing inability to perform basic self-care functions OR Hospitalization indicated
Serum Sickness¹¹	Mild signs and symptoms	Moderate signs and symptoms AND Intervention indicated (e.g., antihistamines)	Severe signs and symptoms AND Higher level intervention indicated (e.g., steroids or IV fluids)	Life-threatening consequences (e.g., requiring pressor or ventilator support)

⁹ Definition: A disorder characterized by nausea, headache, tachycardia, hypotension, rash, and/or shortness of breath.

¹⁰ For pain associated with injections or infusions, see the *Site Reactions to Injections and Infusions* section (page 23).

¹¹ Definition: A disorder characterized by fever, arthralgia, myalgia, skin eruptions, lymphadenopathy, marked discomfort, and/or dyspnea.

Systemic

PARAMETER	GRADE 1 MILD	GRADE 2 MODERATE	GRADE 3 SEVERE	GRADE 4 POTENTIALLY LIFE- THREATENING
Underweight ¹² > 5 to 19 years of age	NA	WHO BMI z-score < -2 to ≤ -3	WHO BMI z-score < -3	WHO BMI z-score < -3 with life-threatening consequences

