### 8.3 Other safety parameters

#### 8.3.1 Vital signs data

Blood pressures (diastolic [DBP] and systolic [SBP]; mmHg), respiratory rate (breaths/min), body temperature (°C) and pulse rate (bpm) will be measured (see section [12.1](#)) for each cohort at the screening visit, Day 1, Week 1 and then once a week thereafter.

Raw data and changes from baseline (Day 1 pre-dose) will be described by measurement time, for each cohort.

A summary table with the number and percentage of subjects with PCSA values (defined in section [12.2](#)) will be generated by measurement time, for each cohort.

A specific listing of all values of a parameter over time for any parameter with PCSA values with clinical significance information will be generated.

Pulse rate, DBP, and SBP are classified in the following abnormality codes:

	Pulse (bpm)	DBP (mmHg)	SBP (mmHg)
Abnormally low	≤ 50	≤ 50	≤ 90
Abnormally high	≥ 120	-	-
Grade 1 or mild	-	> 90 - < 100	> 140 - < 160
Grade 2 or moderate	-	≥ 100 - < 110	≥ 160 - < 180
Grade 3 or severe	-	≥ 110	≥ 180

A summary table with the number and percentage of subjects with abnormal values (as defined above) will be generated for each cohort for the worst post-baseline value. The same table will be provided by measurement time.

A specific listing of all values of a parameter over time for any parameter with abnormal values with clinical significance information will be generated.

Values (raw data and changes from baseline) will be listed and PCSA and abnormal values will be flagged with clinical significance information.

Graph of mean (SE) by cohort over time will be plotted.

In determining the abnormalities, the following rules are applied:

- Worst grades/abnormalities are determined over the whole observational period, including post-baseline scheduled and unscheduled measurements.

- The abnormalities ‘abnormally low’ and ‘abnormally high’/grades are considered equally important, i.e. if a subject has an ‘abnormally low’ as well as an ‘abnormally high’ or graded post-baseline value, both abnormalities are shown in the tables. (This means that the sum of the percentages can be more than 100%.)

Definition treatment-emergent:

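### The Grade 3 rash criterion prints two unequal fever limits, 38°C and 100°F (37.78°C), so the threshold for mandatory action has no single value

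*Protocol*

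**What the plan says.** Protocol Section 7.6 grades rash on a WHO scale. Under Grade 3, any cutaneous event qualifies if it has one item from a short list, and one of those items is "fever >38°C or 100°F". Table 7-1 and the running text of Section 7.6 carry the same wording.

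The Grade 3 action in Table 7-1 is "Permanently discontinue the intake of SMV", with no rechallenge. Odalasvir (ODV) and AL-335 may go on together at the investigator's discretion. The text of Section 7.6 adds, for Grades 3 and 4, a required on-site visit with safety laboratory tests, local tests on Days 0 and 1, and a required dermatology referral. These requirements are not restricted to subjects taking SMV. At Grades 1 and 2, continuing the study drugs is left to the investigator. At Grade 2, referral is optional.

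Appendix F, in the fever row of its Systemic table, gives Grade 1 fever as "38.0 to < 38.6°C or 100.4 to < 101.5°F". SAP Section 8.3.1 reports body temperature in degrees Celsius only.

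**The concern.** The rash line reads like one limit given in two units, but the units do not convert to each other. One limit is printed as 38°C and the other is 37.78°C. Fever alone moves a cutaneous event to Grade 3, so this figure decides whether several actions are compulsory or discretionary. The protocol allows up to 50 sites globally. A site reading in Celsius and a site reading in Fahrenheit could grade the same subject differently while both follow the text.

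For the subject, the issue is whether SMV must be stopped for good and whether the Grade 3 work-up must be done. For the analysis, it is whether an event counts as Grade 3 on the WHO scale.

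**Working it through.** **Inputs.** The rash limits of 38°C and 100°F are from Protocol Section 7.6 (Table 7-1 and text). The fever bounds are from Appendix F. I take the greater-than sign to apply to both rash figures.

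**1. The printed equivalence.** With °C = (°F − 32) / 1.8 and °F = °C × 1.8 + 32:

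- 100°F: (100 − 32) / 1.8 = 37.78°C
- 38°C: 38 × 1.8 + 32 = 100.4°F
- Difference: 38 − 37.78 = 0.22°C, or 100.4 − 100 = 0.4°F

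The equivalence is not reproduced.

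**2. Same conversion applied to Appendix F.**

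| Printed °C | Printed °F | Converted °F |
|---|---|---|
| 38.0 | 100.4 | 100.40 |
| 38.6 | 101.5 | 101.48 |
| 39.3 | 102.7 | 102.74 |
| 40.0 | 104.0 | 104.00 |

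All four pairs agree to rounding. The mismatch is therefore confined to the rash rule. It appears there in both the table and the text, so damage in reading the PDF is an unlikely cause.

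**3. Readings in the gap.** Temperatures above 37.78°C and not above 38.0°C meet the Fahrenheit limit only. In 0.1°C steps these are 37.8, 37.9 and 38.0°C.

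**4. What turns on the grade (Section 7.6).**

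| | Grade 2 | Grade 3 |
|---|---|---|
| SMV | may continue, investigator's discretion | must stop permanently, no rechallenge |
| Visit | required; telephone contact if a visit is not possible | on-site visit required |
| Laboratory tests | recommended at the first visit, required at later unscheduled visits | required on Days 0 and 1 |
| Dermatologist | optional | required |

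Only the first row depends on SMV being in the regimen.

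**5. Who could still come under the rule.** Section 1.2.1.2 reports 123 subjects dosed by 6 February 2017, and the ceiling is 320, so at most 320 − 123 = 197 remain to be dosed. Cohorts 7 to 12, all planned with SMV 75 mg, account for 6 × 10 = 60 to 6 × 20 = 120 of these if all are opened. Cohort 6 could add up to 20 − 11 = 9. These are nominal cohort sizes, since a cohort may be enlarged after a regimen change. They bound the subjects at risk of the ambiguity. The number of cases that would turn on it cannot be obtained from the documents.

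**The case against.** The strongest reply is that the wording already resolves itself. In a list where any one item is enough, either temperature is enough. The lower limit then governs, the rule errs toward stopping SMV, and nobody is less protected. This reading is possible, but the text does not settle on it. Appendix F uses the same word to join one limit in two units, which suggests that the rash line was meant the same way and that 100°F is a rounding slip.

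The cautious reading also has a cost. Stopping SMV leaves AL-335 with ODV, the two-drug regimen on which enrolment in Cohort 4 was halted after relapses. Eight-week SVR24 in non-cirrhotic genotype 1 was 18/20 (Cohort 1b) and 3/5 (Cohort 4) without SMV, against 20/20 (Cohort 2) with it at the same AL-335 and ODV doses. These comparisons are non-randomised and concern full courses, so they show only that an unnecessary stop may have a price.

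A second reply is that the intended value cannot be known. This stands. The WHO scale behind the rash grades is not reproduced in the documents, and writing 38.0°C raises the lowest limit now printed. Appendix F supports the pairing of units only: its Grade 1 fever includes exactly 38.0°C, whereas the rash rule uses a strict inequality.

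A third reply points to the Appendix F instruction for events between two grades, that "sites should select the higher of the two grades". It leans toward Grade 3, but it belongs to the DAIDS table and the rash grades here are WHO grades.

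Finally, the difference between grades is modest in practice. Grade 2 already calls for a visit. Section 7.6 allows standard management where the rash is most likely due to concomitant illness or a non-study drug. Section 4.6.1 requires stopping whenever the investigator believes, for safety reasons, that "it is in the best interest of the subject to discontinue study drug treatment". All of this stands, and it limits the size of the problem without giving the threshold one value.

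**Conclusion.** The point holds as a minor correction to a safety rule. A threshold for mandatory action is printed with two values 0.22°C apart, and no text says which one governs. The conversion is certain; the intended value is not. Cases that turn only on this gap are likely to be very few.

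No sample size or efficacy analysis changes. SAP Section 8.1 does summarise events of special interest, including rash, by WHO toxicity grade, and tabulates events leading to discontinuation of any study drug. A single case in the gap could therefore move one of those counts. DAIDS severity grading is unaffected, because the rash row in Appendix F has no fever criterion.

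Three stronger readings are tempting and are not supported:

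- A reader might infer that the error matters only for stopping SMV in SMV cohorts. Section 7.6 does not limit the Grade 3 visit, laboratory tests or referral to SMV recipients.
- A reader might infer that subjects are left unprotected. The literal reading is the cautious one, and the investigator can stop treatment at any grade.
- A reader might infer that Table 7-1 omits a Grade 3 criterion, since the text of Section 7.6 lists "serum sickness-like reaction" and the table as supplied does not. Loss in reading the table cannot be excluded: its footnote c, "Monotherapy with any of the study drugs is not allowed", has no marker left in the table body. No finding should rest on that difference.

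**What to change.** Print one limit, in the same words, in Table 7-1 and in the Grade 3 text of Section 7.6. The suggested wording is *fever >38.0°C (>100.4°F)*, which uses the unit pairing already in Appendix F and fits the Celsius reporting in the SAP. If the sponsor meant the more cautious limit, print *fever >37.8°C (>100°F)* instead. In that case state which unit governs, because 37.8°C is a rounded figure: 37.8 × 1.8 + 32 = 100.04°F.

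The sponsor should confirm the intended value before the wording is changed, since the first option raises the lower of the two limits now in force. The cost is two lines in the next amendment or a clarification letter to sites. The SAP needs no change.
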